5.1 Cohort Summary

This study will involve a new user, parallel group, cohort study design comparing linagliptin to the 2nd generation sulfonylurea (SU) antidiabetic class as a proxy for placebo. 2nd generation SUs are not known to have an impact on the outcome of interest. In addition, SUs were the most frequent background treatment in CARMELINA (after metformin), and DPP4i and SUs are preferentially prescribed to similarly older patients in real world (Paterno et al., 2019). The patients will be required to have continuous enrollment during the baseline period of 180 days before initiation of linagliptin or a comparator drug (cohort entry date). Follow-up for the outcome (3P-MACE), begins the day after drug initiation. As in the trial, patients are allowed to take other antidiabetic medications during study follow-up.

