5.2 Important steps for cohort formation

5.2.1 Eligible cohort entry dates

Market availability of linagliptin in the U.S. started on May 2, 2011.

- For Marketscan: May 2, 2011-Dec 31, 2017 (end of data availability).
- For Medicare: Jan 1, 2012-Dec 31, 2017 (start- end of data availability).
- For Optum: May 2, 2011-March 31, 2019 (end of data availability).

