Excluded based on Exclusion 11 part 1- life expectancy less than 5 years [using combined comorbidity index as a proxy (365 days)]	-2,263	129,818	-1,125	129,334	-12,200	422,949
Excluded based on Exclusion 11 part 2- History of Malignant Neoplasm (within last 3 years)	-4,153	125,665	-4,128	125,206	-14,241	408,708
Excluded based on Exclusion 12- ACS/unstable angina (≤ 2 months prior)	-374	125,291	-332	124,874	-788	407,920
Excluded based on Exclusion 13- Stroke or TIA (≤ 3 months prior)	-2,292	122,999	-1,981	122,893	-7,081	400,839
Final cohort		122,999		122,893		400,839

* Medicare database includes only patients ≥ 65 years of age with at least one diagnosis for diabetes, heart failure, or stroke.

** Exclusion 8 and Exclusion 10 collapsed for adherence to CMS suppression guidelines.

6. Variables

6.1 Exposure-related variables:

Study drug:

The study exposure of interest is initiation of linagliptin. Initiation will be defined by no use of linagliptin or a comparator in the prior 6 months before treatment initiation (washout period).

Comparator agents:

- Initiators of linagliptin will be compared to initiators of-
 - 2nd generation sulfonylureas

Because linagliptin and comparators are frequently used as second or third line treatments of T2DM, we expect it to be unlikely that linagliptin and comparators are initiated in patients with substantially different baseline risk for proposed outcomes.

6.2 Preliminary covariates:

- Age
- Sex
- Combined Comorbidity Index (CCI), measured over the baseline covariate assessment period, defined as 180 days prior to and including index date

Covariates listed above represent only a small subset of covariates that will ultimately be controlled for in the design and analysis. We use the covariates above only for initial feasibility analyses to judge whether there is likely to be sufficient overlap between treatment groups to proceed with the study. Remaining covariates are defined only after the study has passed the initial feasibility analysis and the initial power assessment and are listed in Table 1 (**Appendix B**). These covariates are based on those used by Patorno et al. (2019).

6.3 Outcome variables and study follow-up:

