Appendix A

	6) Body Mass Index (BMI) ≥ 45 kg/m ² at visit 1 (screening).	Measured 180 days prior to drug initiation any diagnosis position in inpatient or outpatient care setting: Excluding patients with ICD-9 Diagnosis Code (any position) is any of: {"278.01"} 278.01-MORBID OBESITY	
	7) Signed and dated written informed consent by date of visit 1 (screening) in accordance with GCP and local legislation prior to any study related procedure.	N/A	-
	8) High risk of CV events (I and/or II):		
I	Albuminuria (UACR ≥ 30 mg/g creatinine or ≥ 30 µg/min [microgram albumin per minute] or ≥ 30 mg/24 h [milligram albumin per 24 hours] in two out of three unrelated spot urine or timed samples in the last 24 months prior to randomization)* AND previous macrovascular disease, defined as either one or more:		
Ia	Confirmed history of MI (>2 months prior to Visit 1)	Measured from the start of all available data to on the date of drug initiation with diagnosis/procedure position and care setting as noted below:	

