	
11) Patients considered unreliable by the investigator concerning the requirements for follow-up during the study and/or compliance with study drug administration, have a life expectancy less than 5 years for non-CV causes, or have cancer other than non-melanoma skin cancer within last 3 years, or has any other condition than mentioned which in the opinion of the investigator, would not allow safe participation in the study.
	
Measured over 365 days prior to drug initiation: CCI \geq10 OR
 
Measured 1095 days prior to drug initiation in any diagnosis position in inpatient and outpatient care setting: History of malignant neoplasm ICD-9: 140.xx-208.xx (except 173.xx, non-melanoma skin cancer)- in prior 3 years
	
"Gagne, Josh J et. al. ""A combined comorbidity score predicted mortality in elderly patients better than existing scores." J Clin Epidemiol. 2011 Jul;64(7):749-59. doi: 10.1016/j.jclinepi.2010.10.004.
 
Sun, Jenny W et. al. ""Validation of the Combined Comorbidity Index of Charlson and Elixhauser to Predict 30-Day Mortality Across ICD-9 and ICD-10." Med Care. 2018 Sep;56(9):812. doi: 10.1097/MLR.0000000000000954."

	
12) Acute coronary syndrome (ACS), diagnosed \leq 2 months prior to visit 1 (screening).
	
Measured 60 days prior to drug initiation in any diagnosis position in inpatient and outpatient care setting: ACS/unstable angina 411.xx
	
Patorno, Elisabetta et al. "Cardiovascular outcomes associated with canagliflozin versus other non-gliflozin antidiabetic drugs: population based cohort study." BMJ 2018;360:k119 http://dx.doi.org/10.1136/bmj.k119
 
Patorno, Elisabetta et al. "Empagliflozin and the Risk of Heart Failure Hospitalization in Routine Clinical Care: A First Analysis from the Empagliflozin Comparative Effectiveness and Safety (EMPRISE) Study." Circulation. 2019 Apr 8. doi: 10.1161/CIRCULATIONAHA.118.039177

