...median [IQR]	4.50 [4.20, 4.80]	4.50 [4.20, 4.80]	4.30 [4.00, 4.70]	4.40 [4.07, 4.70]	N/A	N/A	4.48 (0.46)	4.49 (0.46)	-0.02
...Missing; n (%)	5,089 (57.3%)	4,953 (55.8%)	8,193 (94.0%)	8,267 (94.8%)	N/A	N/A	13,282 (75.5%)	13,220 (75.1%)	0.01
Comorbidity Scores									
CCI (180 days)- ICD9 and ICD10									
...mean (sd)	3.36 (2.08)	3.35 (2.10)	2.46 (1.88)	2.45 (1.86)	3.77 (2.14)	3.77 (2.11)	3.47 (2.09)	3.47 (2.07)	0.00
...median [IQR]	3.00 [2.00, 5.00]	3.00 [2.00, 5.00]	2.00 [1.00, 4.00]	2.00 [1.00, 4.00]	4.00 [2.00, 5.00]	4.00 [2.00, 5.00]	3.48 (2.09)	3.48 (2.07)	0.00
Frailty Score: Qualitative Version 365 days as Categories, v1									
...0; n (%)	4,324 (48.7%)	4,263 (48.0%)	2,619 (30.0%)	2,596 (29.8%)	9,977 (29.9%)	9,686 (29.1%)	16,920 (33.2%)	16,545 (32.5%)	0.01
...1 to 2; n (%)	2,752 (31.0%)	2,873 (32.4%)	3,661 (42.0%)	3,717 (42.6%)	10,036 (30.1%)	10,218 (30.7%)	16,449 (32.3%)	16,808 (33.0%)	-0.01
...3 or more; n (%)	1,804 (20.3%)	1,744 (19.6%)	2,436 (27.9%)	2,403 (27.6%)	13,306 (39.9%)	13,415 (40.3%)	17,546 (34.5%)	17,562 (34.5%)	0.00
Frailty Score: Empirical Version 365 days as Categories,									
...<0.12908; n (%)	1,119 (12.6%)	1,228 (13.8%)	1,240 (14.2%)	1,338 (15.4%)	1,500 (4.5%)	1,563 (4.7%)	3,859 (7.6%)	4,129 (8.1%)	-0.02
...0.12908 - 0.1631167; n (%)	2,577 (29.0%)	2,521 (28.4%)	2,640 (30.3%)	2,578 (29.6%)	5,589 (16.8%)	5,398 (16.2%)	10,806 (21.2%)	10,497 (20.6%)	0.01
...>=0.1631167; n (%)	5,184 (58.4%)	5,131 (57.8%)	4,836 (55.5%)	4,800 (55.1%)	26,230 (78.7%)	26,358 (79.1%)	36,250 (71.2%)	36,289 (71.3%)	0.00
Non-Frailty; n (%)	4,985 (56.1%)	5,157 (58.1%)	4,680 (53.7%)	4,703 (54.0%)	1,469 (4.4%)	1,398 (4.2%)	11,134 (21.9%)	11,258 (22.1%)	0.00
Frailty Score (mean): Qualitative Version 365 days, v1									
...mean (sd)	1.34 (1.92)	1.33 (1.90)	1.80 (1.89)	1.79 (1.89)	2.36 (2.43)	2.36 (2.39)	2.09 (2.26)	2.08 (2.23)	0.00
...median [IQR]	1.00 [0.00, 2.00]	1.00 [0.00, 2.00]	1.00 [0.00, 3.00]	1.00 [0.00, 3.00]	2.00 [0.00, 4.00]	2.00 [0.00, 4.00]	1.65 (2.26)	1.65 (2.23)	0.00
Frailty Score (mean): Empirical Version 365 days,									
...mean (sd)	0.19 (0.06)	0.18 (0.06)	0.17 (0.05)	0.17 (0.05)	0.21 (0.07)	0.21 (0.07)	0.20 (0.07)	0.20 (0.07)	0.00
...median [IQR]	0.17 [0.14, 0.21]	0.17 [0.14, 0.21]	0.16 [0.14, 0.20]	0.16 [0.14, 0.19]	0.20 [0.17, 0.25]	0.20 [0.17, 0.25]	0.19 (0.07)	0.19 (0.07)	0.00
Healthcare Utilization									

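### Exclusion 11 and several covariates look back 365 or 1,095 days, but entry guarantees only 180 days and the propensity score holds no measure of available history

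*Combined protocol and SAP*

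**What the plan says.** - **Guaranteed history.** Section 5.1 requires "continuous enrollment during the baseline period of 180 days before initiation of linagliptin or a comparator drug". The flowchart in Section 5.3 applies this as a six-month registration step. No later step asks for 12 or 36 months.
- **Exclusion 11.** In Appendix A the comorbidity part (CCI of 10 or more) is "Measured over 365 days prior to drug initiation" and the malignancy part is "Measured 1095 days prior to drug initiation in any diagnosis position in inpatient and outpatient care setting". The flowchart in Section 5.3 repeats the 365-day and 3-year windows.
- **Covariates.** Table 1 in Appendix B lists "Frailty Score: Qualitative Version 365 days as Categories, v1", the empirical frailty score over the same period, and hypertension from claims within 365 days. The CCI covariate, by contrast, covers 180 days.
- **Inclusion 8.** The cardiovascular-history items in Appendix A are "Measured from the start of all available data to on the date of drug initiation".
- **Medicare data.** Section 5.2.1 reads "For Medicare: Jan 1, 2012-Dec 31, 2017 (start- end of data availability", so the entry window opens on the first day of data.
- **Propensity score.** Section 9 puts the full covariate list into the PS, apart from laboratory values. Table 1 shows no index date or calendar year, no length of prior enrollment and no cancer variable. Nothing in the document says how patients with less than 365 or 1,095 days of history are handled.

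**The concern.** Take two patients whose only cancer code is 14 months old. One has been enrolled for 7 months and is kept, because the code is not visible. The other has been enrolled for 3 years and is removed. They differ only in how long the database has observed them. The same applies to a CCI of 10 or more that rests on codes between 180 and 365 days old, and to the 365-day frailty and hypertension values. Under Inclusion 8 the dependence runs the other way: more history makes it easier to qualify.

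This matters for the hazard ratio if available history differs between linagliptin and sulfonylurea initiators. That is possible when a drug marketed from May 2011 is compared with an established class. Eligibility and the 365-day covariates would then be misclassified to a different degree in each arm. Good balance on those recorded covariates would not show it, because the recorded values are themselves what is affected.

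**Working it through.** **1. The plan's own figures.** The Exclusion 11 subtractions in Section 5.3 are exact:

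| Database | Before | CCI step | Cancer step | After |
|---|---|---|---|---|
| Optum | 132,081 | −2,263 | −4,153 | 125,665 |
| MarketScan | 130,459 | −1,125 | −4,128 | 125,206 |
| Medicare | 435,149 | −12,200 | −14,241 | 408,708 |

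The power figures in Section 10 are reproduced by power = Φ(ln 1.3 × √(D/4) − 1.96), where D = 2 × patients per arm × risk. For the pooled table D = 2 × 50,915 × 0.02591 = 2,638.4, which gives 0.999999116 as printed. For Medicare D = 2 × 33,319 × 0.04247 = 2,830.1, which gives 0.99999974 as printed.

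**2. When the look-backs become possible in Medicare** (data start from Section 5.2.1, baseline from Section 5.1):

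- Earliest entry: 1 Jan 2012 + 180 days = 29 Jun 2012.
- Full 365 days first possible: 1 Jan 2012 + 365 days = 31 Dec 2012.
- Full 1,095 days first possible: 1 Jan 2012 + 1,095 days = 31 Dec 2014.
- Possible entry days, 29 Jun 2012 to 31 Dec 2017 inclusive: 2,012.
- Days on which nobody can have 365 days of history: 185 / 2,012 = 9.2%.
- Days on which nobody can have 1,095 days of history: 915 / 2,012 = 45.5%.

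These limits hold whatever the patient's own enrollment. Shorter individual enrollment can truncate the window at later dates too. The document gives no data start for Optum or MarketScan, so there the dependence can be traced only to individual enrollment length.

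**3. Who is affected.** Codes in the last 180 days are visible for everyone. A patient is misclassified on malignancy only if every cancer code in the past 1,095 days is older than the observed history. The document does not give that number.

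**4. What a long-history run would retain.** If Medicare entries were spread evenly over the 2,012 days (an assumption, since the distribution is not printed), and only the calendar limit counted, 54.5% would remain. That is 2,830.1 × 0.545 ≈ 1,543 events and power 0.9993. Individual enrollment would cut this further. If 75%, 50% or 25% of the printed 2,638.4 pooled events remained, power would be 0.9999, 0.997 or 0.921.

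**The case against.** The protocol aims to follow the trial criteria closely, and the trial criterion is cancer within three years. Using whatever history exists is a defensible way to approach that, and better than discarding it. Cancer codes count in any position and any care setting, so a patient with a cancer code in the past six months is always caught. Covariates with a uniform window balance well after matching: the pooled 180-day CCI is 3.47 in both arms, hospitalizations are 0.15 in both, and distinct medications are 11.26 against 11.25. No difference in history between arms is shown.

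Most of this stands. It argues against shortening the windows and limits the affected group to patients with older codes only. It does not show that the arms have similar history, because none of the balanced items measures that.

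A reader might infer under-detection from the cancer step, which removes 3.4% in Medicare (14,241 / 422,949) and 3.2% in each commercial database, although matched Medicare linagliptin patients are on average 9 to 12 years older. The documents do not support this. The CCI step runs first and had already removed 2.8% in Medicare, against 1.7% in Optum and 0.9% in MarketScan. Exclusion 11 as a whole removed 26,441 / 435,149 = 6.1% in Medicare, against 6,416 / 132,081 = 4.9% and 5,253 / 130,459 = 4.0%. The commercial databases also guarantee only 180 days, so they are no clean benchmark.

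**Conclusion.** The mismatch is real and should be dealt with before the hazard ratio is estimated. For patients whose relevant codes are older than 180 days, eligibility under Exclusion 11 and the 365-day covariates depend on a quantity that the plan neither reports nor adjusts for. In Medicare, which supplies 33,319 of the 50,915 matched pairs, the full malignancy window is impossible on 915 of 2,012 entry days. This rests on the printed data start and on the 180-day requirement being the only history requirement.

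Three stronger readings go beyond the documents:

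- The 45.5% is a share of calendar days. It is not the share of Medicare patients affected, because entry dates are not printed.
- Because the mortality component is not yet limited to cardiovascular causes, a reader might infer that missed cancers pass straight into the composite. Neither the number missed nor any difference by arm is given, and median as-treated follow-up is only 118 to 137 days overall.
- Section 5.2.1 might seem to admit Medicare patients from 1 January 2012 without a baseline. The six-month registration step already prevents this, so the date needs no correction.

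A bias in the hazard ratio is therefore possible but not shown, and its direction and size cannot be determined.

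**What to change.** 1. Before the comparative analysis in Section 13, whose date is still blank, derive the days of continuous enrollment available before cohort entry. Add this variable to the PS in each database, report it by arm in Table 1, and re-match. It does not recover unseen diagnoses, but it shows whether the arms had the same chance of having them seen, and it brings the arms together if they did not. Adding it requires no eligibility change. The cost is one derived variable, one re-match, and updated balance and power figures in Sections 9 and 10.
2. Prespecify in Section 13.2 a sensitivity analysis restricted to patients with at least 1,095 days of prior enrollment, in whom Exclusion 11 operates as stated. The cost is one extra run with fewer events. On the assumptions above, pooled power stays above 0.9 even if only a quarter of the printed events remain. The Optum and MarketScan results would be imprecise on their own, since their full-cohort powers are only 0.61 and 0.66.

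If history turns out to be similar in the two arms, the new Table 1 row largely settles the point.

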5.2.2 Specify inclusion/exclusion criteria for cohort entry and define the index date

Inclusion and exclusion criteria were adapted from the trial as closely as possible. Definitions for all inclusion/exclusion are provided in **Appendix A** and are summarized in the flowcharts below.

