	The primary outcome is the time to the first occurrence of CV death, non-fatal myocardial infarction (MI) or non-fatal stroke—the so-called 3-point major adverse CV events (3P-MACE) composite outcome.	
Measured 1 days after drug initiation in diagnosis position specified below and inpatient care setting:
 
Inpatient mortality/MI/Stroke –
 
For MI Any diagnosis position in inpatient care setting ICD-9 Dx 410.X (acute myocardial infarction) excluding 410.x2 (subsequent episode of care)
 
For stroke Primary diagnosis position in inpatient care setting ICD-9 discharge diagnosis: 430.xx Subarachnoid hemorrhage (SAH) 431.xx Intracerebral hemorrhage (ICH) 433.x1 Occlusion and stenosis of precerebral arteries with cerebral infarction 434.xx (excluding 434.x0) Occlusion and stenosis of cerebral arteries with cerebral infarction 436.x Acute, but ill-defined cerebrovascular events
 
Mortality- See Mortality Sheet.
	
For MI:
 
►PPV 94% in Medicare claims data [Kiyota Y, Schneeweiss S, Glynn RJ, Cannuscio CC, Avorn J, Solomon DH. Accuracy of Medicare claims-based diagnosis of acute myocardial infarction: estimating positive predictive value on the basis of review of hospital records. American heart journal 2004;148:99-104.]
 
►PPV 88.4% in commercially-insured population [Wahl PM, Rodgers K, Schneeweiss S, et al. Validation of claims-based diagnostic and procedure codes for cardiovascular and gastrointestinal serious adverse events in a commercially-insured population. Pharmacoepidemiology and Drug Safety 2010;19:596-603.]
 
For stroke:
 
PPV of 85% or higher for ischemic stroke PPV ranging from 80% to 98% for hemorrhagic stroke
 
 
 
	Can't be measured in claims but not important for the analysis
	INCLUSION CRITERIA			

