Ib	Advanced coronary artery disease, defined by any one of the following: • ≥ 50% narrowing of the luminal diameter in 2 or more major coronary arteries by coronary angiography, MRI angiography or CT angiography; Definition of major coronary arteries: LAD (Left Anterior Descending), CX (Circumflex) or RCA (right coronary artery) • Left main stem coronary artery with ≥ 50% narrowing of the luminal diameter by coronary angiography, MRI angiography or CT angiography; • Prior percutaneous or surgical revascularization of ≥ 2 major coronary arteries at least 2 months prior to Visit 1 (screening); • The combination of prior percutaneous or surgical revascularization of 1 major coronary artery at least 2 months prior to visit 1 (screening), and ≥ 50% narrowing of the luminal diameter by coronary angiography, MRI angiography or CT angiography of at least 1 additional major coronary artery.	Ischemic heart disease in any diagnosis position and inpatient or outpatient care setting: ICD-9 410.xx-414.xx OR Previous cardiac procedure (CABG or PTCA or Stent) in any procedure position and care setting defined below: PTCA: Inpatient CPT-4: 92973, 92982, 92984, 92995, 92996, 92920 – 92921, 92924 – 92925, 92937, 92938, 92941, 92943, 92944 OR – Inpatient or outpatient ICD-9 procedure: 00.66, 36.01, 36.02, 36.03, 36.05, 36.09 Stenting: Inpatient CPT-4: 92980, 92981, 92928 – 92929, 92933 - 92934 OR – Inpatient or outpatient ICD-9 procedure: 36.06, 36.07 CABG: Inpatient CPT-4: 33510 – 33536, 33545, 33572. OR – Inpatient or outpatient ICD-9 procedure: 36.1x, 36.2x Transmyocardial revascularization: Inpatient or Outpatient CPT-4: 33140, 33141 OR -Inpatient or outpatient ICD-9 procedure: 36.31-36.34	Patorno, Elisabetta et al. "Cardiovascular outcomes associated with canagliflozin versus other non-gliflozin antidiabetic drugs: population based cohort study." BMJ 2018;360:k119 http://dx.doi.org/10.1136/bmj.k119 Patorno, Elisabetta et al. "Empagliflozin and the Risk of Heart Failure Hospitalization in Routine Clinical Care: A First Analysis from the Empagliflozin Comparative Effectiveness and Safety (EMPRISE) Study." Circulation . 2019 Apr 8. doi: 10.1161/CIRCULATIONAHA.118.039177

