Ic	High-risk single-vessel coronary artery disease, defined as the presence of ≥ 50% narrowing of the luminal diameter of one major coronary artery by coronary angiography, MRI angiography or CT angiography in patients not revascularized: AND at least one of the following: • A positive non invasive stress test, confirmed by either: o a positive ECG exercise tolerance test in patients without left bundle branch block, Wolff-Parkinson-White syndrome, left ventricular hypertrophy with repolarization abnormality, or paced ventricular rhythm, atrial fibrillation in case of abnormal ST-T segments; o a positive stress echocardiogram showing induced regional systolic wall motion abnormalities; o a positive nuclear myocardial perfusion imaging stress test showing stress- induced reversible perfusion abnormality; o a positive cardiac stress perfusion MRI showing a stress induced perfusion defect; • Patient discharged from hospital with a documented diagnosis of unstable angina pectoris between 2 and 12 months prior to visit 1 (screening).		
Id	History of ischemic or haemorrhagic stroke (>3 months prior to visit 1)	Measured from the start of all available data to on the date of drug initiation in any diagnosis position and procedure position in inpatient or outpatient care setting: Any stroke ICD-9 Dx: 430.xx, 431.xx, 433.xx, 434.xx, 436.xx	We including anytime prior to drug initiation here, but then any patients with any stroke within last 3 months are excluded due to the last exclusion criteria.

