Appendix A

	
5) Any previous (or planned within next 12 months) bariatric surgery (open or laparoscopic) or intervention (gastric sleeve).
	
Measured 180 days prior to drug initiation in any procedure position in inpatient or outpatient care setting: Any history CPT-Code-Abbreviation Procedure 43644 -LRYBG- Laparoscopic Roux-en-Y gastric bypass (Roux limb 150 cm or less) 43645 -LRYGBX- Laparoscopic gastric bypass with small intestine reconstruction to limit absorption 43770 -LAGB- Laparoscopic adjustable gastric band 43846 -ORGB- Open Roux-en-Y gastric bypass (Roux limb 150 cm or less) 43847 -ORGBX- Open gastric bypass with small intestine reconstruction to limit absorption
	
Patorno, Elisabetta et al. "Cardiovascular outcomes associated with canagliflozin versus other non-gliflozin antidiabetic drugs: population based cohort study." BMJ 2018;360:k119 http://dx.doi.org/10.1136/bmj.k119
 
Patorno, Elisabetta et al. "Empagliflozin and the Risk of Heart Failure Hospitalization in Routine Clinical Care: A First Analysis from the Empagliflozin Comparative Effectiveness and Safety (EMPRISE) Study." Circulation. 2019 Apr 8. doi: 10.1161/CIRCULATIONAHA.118.039177

	
6) Pre-planned coronary artery re-vascularization (PCI, CABG) or any previous PCI and/or CABG \leq 2 months prior informed consent
	
Measured 60 days prior to drug initiation in any diagnosis position and procedure position in care settings indicated below: (\leq 2 months) PTCA: Inpatient CPT-4: 92973, 92982, 92984, 92995, 92996, 92920 – 92921, 92924 – 92925, 92937, 92938, 92941, 92943, 92944 OR – Inpatient or outpatient: ICD-9 procedure: 00.66, 36.01, 36.02, 36.03, 36.05, 36.09
 
Stenting: Inpatient CPT-4: 92980, 92981, 92928 – 92929, 92933 - 92934 OR – Inpatient or outpatient ICD-9 procedure: 36.06, 36.07
 
CABG: Inpatient CPT-4: 33510 – 33536, 33545, 33572. OR – Inpatient or outpatient ICD-9 procedure: 36.1x, 36.2x
	
Patorno, Elisabetta et al. "Cardiovascular outcomes associated with canagliflozin versus other non-gliflozin antidiabetic drugs: population based cohort study." BMJ 2018;360:k119 http://dx.doi.org/10.1136/bmj.k119
 
Patorno, Elisabetta et al. "Empagliflozin and the Risk of Heart Failure Hospitalization in Routine Clinical Care: A First Analysis from the Empagliflozin Comparative Effectiveness and Safety (EMPRISE) Study." Circulation. 2019 Apr 8. doi: 10.1161/CIRCULATIONAHA.118.039177

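### As printed in ICD-9, the 60-day ACS exclusion (Exclusion 12) omits acute MI (410.xx), so a recent, non-revascularized MI with no 411.xx code stays in the cohort

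*Combined protocol and SAP*

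**What the plan says.** Section 5.2.2 sets the standard: "Inclusion and exclusion criteria were adapted from the trial as closely as possible". Appendix A gives the coding.

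- **Exclusion 12.** The trial criterion is ACS diagnosed within 2 months before screening. The implementation looks back 60 days, any diagnosis position, inpatient and outpatient, for "ACS/unstable angina 411.xx". The Section 5.3 flowchart uses the same label.
- **Inclusion 8, item Ia.** The trial accepts "Confirmed history of MI (>2 months prior to Visit 1"). The implementation window is "Measured from the start of all available data to on the date of drug initiation with diagnosis/procedure position", so it has no 60-day gap.
- **Inclusion 8, item Ib.** The implementation is "Ischemic heart disease in any diagnosis position and inpatient or outpatient care setting", ICD-9 410.xx-414.xx, or a prior cardiac procedure.
- **Exclusion 6.** The trial criterion is "Pre-planned coronary artery re-vascularization (PCI, CABG) or any previous PCI and/or CABG" within 2 months. The implementation lists PTCA, stent and CABG procedure codes over 60 days, and no diagnosis codes.
- **Stroke (Inclusion 8, item Id).** Stroke at any earlier time qualifies, with the note that "any patients with any stroke within last 3 months are excluded due to the last exclusion criteria". Exclusion 13 does this over 90 days.
- **Primary outcome, MI component.** "Any diagnosis position in inpatient care setting ICD-9 Dx 410.X (acute myocardial infarction) excluding 410.x2 (subsequent episode of care").

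Appendix A also says that the ICD-10 lists are held elsewhere and were obtained by mapping from ICD-9.

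**The concern.** The plan treats stroke and MI alike on the inclusion side: a qualifying event may fall at any time up to drug initiation. For stroke, recent events are then removed by a later exclusion. For MI, the exclusion that should do this covers 411.xx only. A 410.xx code a few days before initiation can therefore qualify a patient as high-risk, although trial item Ia accepts MI only if more than 2 months old.

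Two things are at stake. First, the study exists to emulate a named trial, and this departure is not forced by claims data, because the plan already uses the missing code. Second, MI is part of the primary endpoint. A later inpatient claim for the same pre-index MI, coded 410.x0 or 410.x1, could be counted as an outcome; leaving out 410.x2 limits this but does not rule it out.

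**Working it through.** **1. Trace one patient through the printed ICD-9 lists.** Suppose 410.x1 is recorded 20 days before initiation, with no PTCA, stent or CABG code and no 411.xx code.

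| Rule | Codes and window | Result |
|---|---|---|
| Inclusion 8 Ia/Ib | 410.xx-414.xx, all data to initiation | qualifies |
| Exclusion 6 | PTCA, stent, CABG procedures, 60 days | not removed |
| Exclusion 12 | 411.xx, 60 days | not removed |
| Exclusion 13 | stroke and TIA codes, 90 days | not removed |

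No other printed exclusion contains 410.xx.

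**2. Flowchart.** The Exclusion 12 counts are arithmetically sound: Optum 125,665 - 374 = 125,291; MarketScan 125,206 - 332 = 124,874; Medicare 408,708 - 788 = 407,920. They cannot show which codes were used.

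**3. Table 1, before matching (reference + exposed).**

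| | ACS/unstable angina | Acute MI |
|---|---|---|
| Optum | 1,604 + 117 = 1,721 | 2,328 + 211 = 2,539 |
| MarketScan | 1,705 + 125 = 1,830 | 2,429 + 164 = 2,593 |
| Medicare | 4,863 + 443 = 5,306 | 7,206 + 572 = 7,778 |

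Over a common look-back, an ACS variable that contained 410.xx could not be smaller than acute MI. This is consistent with the gap, assuming that the identically labelled row is the Exclusion 12 variable.

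**4. Size.** Matched acute MI: Optum 203 + 211 = 414; MarketScan 156 + 164 = 320; Medicare 583 + 570 = 1,153. The total is 1,887 of 101,830 = 1.85% (942 reference, 945 exposed). The documents do not date these codes. If the row covers 180 days and the same codes, 1,887 is an upper bound. Assumed shares in the last 60 days: 10% gives 189 (0.19%), one third gives 629 (0.62%), 50% gives 944 (0.93%). Exclusions 6 and 12 have already removed some patients with recent MI, so the true share is probably below what even spacing over 180 days (one third) would give.

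**5. Effect of recounting on the HR.** Take the plan's pooled E = 2,638.4 expected events, which already contain any recounts. With N patients and an assumed recount fraction r, split equally by arm, R = N × r and the reference arm's true events are E0 = (E - R)/(1 + HR). Then observed HR = (HR × E0 + R/2)/(E0 + R/2).

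- True HR 1.0: observed 1.000 for any N and r.
- True HR 1.02, N = 629, r = 0.20: R = 125.8; E0 = 2,512.6/2.02 = 1,243.9; observed (1,268.7 + 62.9)/(1,243.9 + 62.9) = 1.019.
- True HR 1.30, N = 629: 1.299 at r = 0.01 and 1.284 at r = 0.20.
- Extreme, all 1,887 and r = 0.20: R = 377.4; at true HR 1.02, observed 1.017; at 1.30, E0 = 2,261.0/2.3 = 983.1 and observed (1,278.0 + 188.7)/(983.1 + 188.7) = 1.252.

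The range r = 1-20% is an assumption; the documents give no figure.

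**6. Power after removal.** Power = Φ(ln(1.3) × √E/2 - 1.96) reproduces the plan's values: Optum 0.6137 (E = 293.9), MarketScan 0.6586 (E = 326.0), pooled 0.999999. Removing one third of the acute MI patients at an assumed 5% or 20% outcome risk gives:

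- Optum, 138 patients: E = 287.0 or 266.3; power 0.604 or 0.572.
- MarketScan, 107 patients: E = 320.6 or 304.6; power 0.651 or 0.629.
- Pooled, even with all 1,887 removed at 20% risk: E = 2,261.0; power 0.99999.

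**The case against.** **ACS is not defined, and a code does not date a diagnosis.** Both are true. Reading ACS to include acute MI is an assumption, though item Ia supports it. A reader might infer that every patient with a 410.xx claim in the window breaches criterion 12. The documents do not support that: the plan describes 410.x2 as a subsequent episode of care, so such a claim may follow an MI more than 2 months old, which Ia accepts. The point holds for new MIs, and the fix should treat 410.x2 separately.

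**The plan only claims to adapt the criteria.** Some trial criteria, such as HbA1c and stable background therapy, are marked not applicable, and the label ACS/unstable angina is open about its content. This stands in part, but recent MI differs because the plan already has a code for it. Appendix A also grades its mappings by colour, and the colours are not visible in the text. Nothing can be concluded about whether this mapping was flagged as approximate.

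**The effect is small and unquantified.** This stands. The affected number could be close to zero. A reader might infer that the primary HR is materially biased. Baseline acute MI is balanced (942 vs 945), the plan assumes HR 1.0 and targets 1.02, and the shift at those values is nil or about 0.001 to 0.003 even at 20% recounting. A later inpatient 410.x1 may also be a true recurrence.

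**The ICD-10 lists may differ.** They are not shown. Because they were mapped from ICD-9, the gap may carry over, but this is unverified for the later part of an entry period that runs to December 2017 or March 2019.

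**Conclusion.** The gap is real in the printed ICD-9 rules: a new acute MI within 60 days of initiation, without a listed revascularization or 411.xx, is removed by no listed exclusion and meets Inclusion 8. This rests on taking ACS to include acute MI. The number affected is unknown: at most 1,887 matched patients (1.85%) if the Table 1 row covers 180 days and the same codes, possibly more if the row is narrower, and probably well below that bound because Exclusions 6 and 12 deplete recent MIs.

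The consequence is mainly fidelity to the trial population. With balanced recounting there is no bias at HR 1.0, a negligible change at 1.02, and dilution toward 1 at higher true HRs (1.30 would appear as 1.284 with 629 patients and 20% recounted). That direction favours non-inferiority, but it is slight except under extreme assumptions. The point should be corrected before analysis; it does not threaten the primary conclusion.

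**What to change.** Before the comparative analysis:

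- Add 410.x0 and 410.x1 and their ICD-10 equivalents to the 60-day Exclusion 12, up to and including the index date. Handle 410.x2 in a sensitivity analysis.
- Show the ICD-10 lists for Exclusion 12 and for the MI outcome.
- Re-run the flowchart, PS match, Table 1 and power, and report the number removed by arm.

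If the reviewed cohort is kept as primary, state the departure from criterion 12, report the 60-day 410.xx count by arm, and pre-specify a sensitivity analysis of the primary endpoint that excludes these patients, with the PS match re-run and balance shown.

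**Cost.** A re-run in three databases and, if the primary cohort changes, a repeat of the balance and power review in Section 10. Section 13 records no comparative analysis yet, so the change can be made without knowledge of results. Pooled power stays above 0.9999. The single-database loss is about 0.01 to 0.04 if one third of the acute MI patients are removed at 5-20% risk, from values that are already low.
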